4.3 Data Handling Conventions

4.3.1 Visit Windowing

For analysis purposes, all by-visit data will be mapped to a visit window to maintain consistency of therapeutic duration among summaries at each time point. The visit that occurs out of window may be analyzed along with data from an earlier or later visit if the trial day falls into a different visit window category. In addition, unscheduled visits that fall into the window for a scheduled visit may be counted along with that visit, such that no data are excluded from potential summaries. In the case of multiple visit results within a visit window, descriptive statistics will be based on non-missing data from a visit closest to the scheduled visit day. Categorical summary will be based on the worst non-missing results. For the current trial, visits will be mapped by trial day as follows:

Table 1 Windowing Schema for Screening and the Treatment Period

Visit Number	Visit	Planned Trial Day	Protocol Allowed Visit Window (days)	Trial Day Window for Analysis (days)
1	Screening	Within 28 days of first treatment	-28 to -1	<1
2	Week 1	1	1	1-11
3	Week 4	22	18-26	12-32
4	Week 7	43	39-47	33-53
5	Week 10	64	60-68	54-74
6	Week 13	85	81-89	75-95
7	Week 16	106	102-110	96-127
8	Week 22	148	144-152	128-169
9	Week 28	190	183-197	170-232
10	Week 40	274	267-281	233-316
11	Week 52	358	351-365	317-396
12	Week 64	442	428-456	397-484
13	Week 76	526	512-540	485-568
14	Week 88	610	596-624	569-652
15	Week 100	694	680-708	> 652

As long-term FU visits only collect concomitant medication and vital status data, no windowing will be needed for this trial phase.

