### 1.5 Trial Procedure Schedule

Trial Procedure	Screening Phase Day -28 to Day 1	Week (3 wk interval +/- 4 days)						Week (6 wk interval +/- 1 wk)		Week (12 wk interval +/- 2 wks)						Long Term FU	
		1	4	7	10	13	16	22	28	40	52	64	76	88	100 EOT 	3-month interval +/- 2 wks	
		Day															
		1	22	43	64	85	106	148	190	274	358	442	526	610	694 EOT		
		Visit															
		1	2	3	4	5	6	7	8	9	10	11	12	13	14		
Trial Procedures																	
Informed Consent 	X																
Demographics	X																
Medical History	X																
Physical Exam incl. vital signs 	X																
Targeted PE incl. vital signs 		X	X	X	X	X	X	X	X	X	X	X	X	X	X	X	
ECOG	X	X	X	X	X	X	X	X	X	X	X	X	X	X	X	X	
ECG 	X																
Eligibility Criteria	X																
Concomitant Medications	X	collected at all clinic visits (including atezolizumab dosing visits)															
Adverse Events 	X	collected at all clinic visits (including atezolizumab dosing visits)														X 	
Survival Status and Auto-immune/ IM clinical manifestation																X	
Tumor Biopsy	X 			X 													
Radiology Assessments																	
CT scan: Thorax, Abdomen and Pelvis 	X				X			X	X	X	X	X	X	X	X	X	

Trial Procedure	Screening Phase Day -28 to Day 1	Week (3 wk interval +/- 4 days)						Week (6 wk interval +/- 1 wk)		Week (12 wk interval +/- 2 wks)						Long Term FU	
		1	4	7	10	13	16	22	28	40	52	64	76	88	100 EOT 	3-month interval +/- 2 wks	
		Day															
		1	22	43	64	85	106	148	190	274	358	442	526	610	694 EOT		
		Visit															
		1	2	3	4	5	6	7	8	9	10	11	12	13	14		
Laboratory Assessments																	
Hematology 	X	X	X	X	X	X	X	X	X	X	X	X	X	X	X	X	
Serum Chemistry 	X	X	X	X	X	X	X	X	X	X	X	X	X	X	X	X	
HIV, HbsAg, HCV	X																
INR, PT, aPTT	X																
Thyroid function test	X	X		X		X											
Biomarker Analyses 	X		X		X			X			X						
Urinalysis	X		X		X		X	X	X	X	X	X	X	X	X	X	
Pregnancy Test 	X	X	X	X	X	X	X	X	X	X	X	X	X	X	X	X	
Dosing																	
Prime Vaccine: MVA-BN-CV301 		X	X														
Boost Vaccine: FPV-CV301 				X	X	X	X	X	X	X	X	X	X	X	X	X	
Atezolizumab		X	X	X	X	X	X										

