### 4.2.3 Long Term Follow-up Period

During the Long-Term follow-up (LTFU) period, subjects will be followed by phone contact at quarterly intervals for survival status assessment and potential autoimmune or immune-mediated clinical manifestations. The FU period may be extended up to 2 years.

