#### **4.2.5.2 Discontinuation from Long Term Follow-up**

All subjects will be followed until death, via telephone contacts at 3 month intervals, to evaluate OS unless the trial is suspended or discontinued. The length of the LTFU is planned to be 2 years, unless all subjects achieve their OS endpoint prior to the end of the 2-year period. If a subject chooses to withdraw from trial survival follow-up, this request must be documented in the source documentation and signed by the investigator. If the subject withdraws from participation in long term telephone follow-up, the trial staff may use a public information source (such as county records) to obtain information about survival status only.

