## 8.3 Reporting

### 8.3.1 Reporting of SAE

All SAEs (initial and FU information) will be reported electronically through the Electronic Data Capture (EDC) platform within 24 hours of the discovery of the event. Manual SAE report forms are available in the Trial Reference Manual, however manual SAE report forms should be forwarded only in the event that electronic capturing is not functioning and must be entered on the AE eCRF when it again becomes available. BN or designee may request FU and other additional information from the Investigator (e.g., hospital admission/discharge notes, laboratory results, etc.).

*The investigator should not delay reporting because of missing information. Nonetheless, the report should be as complete as possible.* This initial notification should include, at a minimum, sufficient information to permit identification of the following:

- The reporter (investigator's name and contact information)
- The subject
- Involved trial product
- AE(s)
- Seriousness criterion and/or criterion for AESI
- Date of onset
- Investigator assessment of causality

The collection of SAE/AESI begins at the time the subject signs informed consent and continues for 30 days following administration of the last dose of trial product for unrelated SAEs/AESIs, and 100 days for related SAEs/AESIs after the last dose of trial product, due to the possibility of a delayed immune effect of anti-PD-1/L1 agent (atezolizumab).

All SAEs, irrespective of the treatment received by the subject, must be reported to BN's PV department within 24 hours of the investigator learning of the event.

All deaths should be reported with the primary cause of death as the SAE term, as death is typically the outcome of the event, not the event itself. The primary cause of death on the autopsy report should be the term reported. Autopsy and postmortem reports must be forwarded to BN's PV department as outlined above.

If trial product is discontinued because of an SAE, this information must be included in the SAE report.

Investigators must report SAEs to their governing IRBs in writing as soon as possible and in accordance with national and local laws and regulations.

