### **8.3.2 Reporting of AESIs**

As noted in [Section 8.1.3](#), IMAEs and cardiac events are considered AESIs as well as the AESI requirements from the manufacturer of Tecentriq®. AESIs occurring throughout the reporting period are to be recorded on the AE eCRF by marking the appropriate tick box as well as the (S)AE/AESI eCRF, regardless of seriousness or attribution. AESIs have to be reported immediately after detection. An automatic email notification will be sent to the relevant project members as soon as an AESI has been reported in the EDC. In addition to the above mentioned eCRFs, an IMAE eCRF is also linked to the (S)AE / AESI eCRF in the EDC and must be completed by the investigator when reporting an IMAE AESI.

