- Related TEAEs, including the following subcategories:
 - TEAEs related to MVA-BN-CV301
 - TEAEs related to FPV-CV301
 - TEAEs related to atezolizumab
 - TEAEs related to trial product
- TEAEs \geq Grade 3
- Related TEAEs \geq Grade 3
- SAEs
- Related SAEs
- AESIs, including IMAEs and Cardiac Events
- Related AESIs
- TEAEs leading to discontinuation of treatment

In addition to the above summary categories, listings will also include the following:

- Baseline Signs and Symptoms
- TEAEs leading to death
- Post-treatment period SAEs and AESIs

A summary table of TEAEs will be created for the following categories: TEAEs, SAEs, AESIs, Related TEAEs, Severe TEAEs, Severe and Related TEAEs, Serious and Related TEAEs, TEAEs leading to discontinuation, and TEAEs leading to death. Event counts and subject incidences will be presented within each category and cohort, as well as overall, for the FAS.

The incidence for the above categories will be calculated as the number of subjects developing the specified AE type, divided by the number of subjects in the cohort. The incidence of AEs will also be calculated within each treatment period.

TEAEs will be summarized by SOC and PT and ordered by descending incidence of SOC, as well as descending incidence of PT within SOC. For TEAEs and related TEAEs, summaries will also be provided by

All AEs will be listed by subject, SOC, and PT. Per protocol, no new AEs should be reported during the LTFU phase, with the exception of related SAEs and related AESIs through 100 days post-last treatment. Any other AEs are reported during the LTFU phase will be listed and flagged as non-treatment emergent, but will not be included in the tables.

For summaries by relationship, CRF relationship categories will be dichotomized as related or unrelated per the above definition. Subjects experiencing more than one TEAE within an SOC or PT will be reported for the highest relationship category for the event of interest.

For summaries by severity, the CTCAE v5.0 grade will be used to summarize severe AEs including AEs \geq Grade 3. Again, if a subject has multiple AEs within an SOC or PT the most severe AE will be counted for the event of interest.

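### Long-term follow-up asks about immune-mediated events for up to 2 years, but the SAP says it does not and leaves events after day 100, or after day 30 if judged unrelated, out of every table

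*SAP*

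**What the plan says.** **What is asked in follow-up.** Protocol 4.2.3: "subjects will be followed by phone contact at quarterly intervals for survival status assessment and potential autoimmune or immune-mediated clinical manifestations". Protocol 4.2.5.2 gives the duration: "The length of the LTFU is planned to be 2 years". The schedule in Protocol 1.5 has a row for it, "Survival Status and Auto-immune/ IM clinical manifestation", marked in the long-term follow-up column. The SAP reproduces the same row in its own schedule (SAP section 3).

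**What must be reported.** Under Protocol 8.3.1, collection of SAEs and AESIs "continues for 30 days following administration of the last dose of trial product for unrelated SAEs/AESIs, and 100 days for related SAEs/AESIs". Footnote 4 to the schedule gives the same two limits and adds a phone contact at day 100. Protocol 8.2.5, without reference to attribution, has SAEs and AESIs documented at every trial visit, the remote follow-up visit included.

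**What the SAP does with it.** SAP 4.3.1: "As long-term FU visits only collect concomitant medication and vital status data, no windowing will be needed for this trial phase". SAP 4.4.8.1: "Per protocol, no new AEs should be reported during the LTFU phase", with an exception for related SAEs and related AESIs to day 100. Other events reported in that phase are to be listed, flagged as not treatment emergent, and kept out of the tables. SAP 4.3.4 likewise excludes from tables the non-serious or unrelated events of days 31 to 100, if any are collected. SAP 4.5 declares no departure from the protocol's analyses.

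**The concern.** Immune-mediated events are one of the two named AESI categories. Protocol 8.1.3 asks for close vigilance for autoimmune phenomena, and Protocol 2.8.1 notes that CV301 is being combined with atezolizumab for the first time. Safety of the combination is a secondary objective. The protocol therefore pays for up to 2 years of targeted questions on delayed immune effects, while the SAP describes that phase as holding no such data and plans no summary of the answers.

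A second difficulty sits inside the window. From day 31 to day 100 an AESI is reportable only if the investigator judges it related. This is an open-label, single-arm trial in which subjects may by then have progressed or started another therapy. Making the causality judgement a condition of reporting can only lower the count of late events, and an event that was not reported cannot be reassessed later.

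At stake is what the trial can say about late immune toxicity.

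**Working it through.** The documents state no figure to reproduce for this point. The check is a comparison of the passages, followed by day arithmetic.

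**1. Passages side by side (days counted from the last dose of trial product)**

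| Immune-mediated event starting | Asked about in follow-up (Protocol 4.2.3)? | Reporting required (Protocol 8.3.1)? | SAP output |
|---|---|---|---|
| Days 31–100, judged related | Yes, once in follow-up | Yes | Treatment emergent by definition and meant to be summarised |
| Days 31–100, judged unrelated | Yes, once in follow-up | No | Listing at most; excluded from tables |
| After day 100, related or not | Yes | No | Listing at most; excluded from tables |

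The second and third rows are the point. The first row is not: those events are defined as treatment emergent in the SAP's General Definitions, and Protocol 9.9.1 also includes them in its summaries.

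SAP 4.3.1 thus contradicts Protocol 4.2.3, the schedule printed in the SAP itself, and the SAP's own day-100 exception. The sentence in SAP 4.4.8.1 follows the reporting windows of Protocol 8.3.1 but attributes to the protocol a position that overlooks 4.2.3.

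**2. Share of follow-up time outside the windows**

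Inputs: follow-up of 2 years = 730 days; windows of 30 days (unrelated) and 100 days (related). The start of follow-up is an assumption, so two cases are shown.

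Share outside = (730 − days of the window that fall within follow-up) / 730.

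- Follow-up starts at the last dose. Related: (730 − 100)/730 = 630/730 = 86%. Unrelated: (730 − 30)/730 = 700/730 = 96%.
- Follow-up starts 30 days after the last dose, as the SAP's phase definitions imply. Related: (730 − 70)/730 = 660/730 = 90%. Unrelated: 730/730 = 100%.

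**3. Quarterly contacts**

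With contacts every 91 days, 730/91 gives about 8 contacts.

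- Start at the last dose: days 91, 182, …, 728. With the allowed ±2 weeks the first falls on days 77 to 105, and the second no earlier than day 182 − 14 = 168.
- Start 30 days later: days 121, 212, …, 758. The first falls no earlier than day 121 − 14 = 107.

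So at most the first of about 8 quarterly contacts lies inside the day-100 window. The separate day-100 phone contact comes on top of these.

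**The case against.** The best defence has four parts.

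- **Nothing reported is lost.** SAP 4.4.8.1 lists other follow-up events and plans a listing of post-treatment SAEs and AESIs; SAP 4.4.1 lists all eCRF data. With at most 68 subjects, a listing shows each case. This stands: a reader might infer that late events have no form and are never recorded, but the eCRF is not among the documents, and no passage says that the immune-event page closes at day 100. What can be said is that these events are untabulated, and that reporting the unrelated ones of days 31 to 100 is not required.
- **The 30/100-day rule is a deliberate design.** It is stated consistently in both documents. It is also softened: SAP 4.4.8.1 counts as related anything possible, probable or definite, or with attribution missing, and for any one of three products. This stands as well. A reader might take the words "regardless of seriousness or attribution" in Protocol 8.3.2 as a demand for attribution-free collection to day 100. That sentence applies only within the reporting period, which 8.3.1 itself sets by attribution. The tension that remains is with Protocol 8.2.5.
- **SAP 4.3.1 is a windowing rule** and decides no adverse event output. True, but its premise is still wrong, and the exclusion from tables in 4.4.8.1 operates without it.
- **The safety endpoint is treatment-emergent events**, and no endpoint names the follow-up immune question. Also true; but data solicited for up to 2 years on a named AESI should either have a summary or be declared as listing-only.

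**Conclusion.** The point holds in this form. The SAP misdescribes what long-term follow-up collects, and its output rules leave solicited immune-mediated events starting after day 100, or after day 30 if judged unrelated, with a listing at most. Protocol 8.2.5 and 8.3.1 also need to be reconciled on whether AESIs of days 31 to 100 are recorded whatever their attribution.

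In time, the gap is 86% to 90% of follow-up for related events and 96% to 100% for unrelated ones, assuming the full 2 years and the two starting points shown. These are not shares of events.

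A reader might go on to estimate the subjects affected from the 12% immune-mediated event rate cited in Protocol 2.1: 0.12 × 68 = 8.2 subjects, or 0.12 × 27 = 3.2 at the minimum enrolment. The documents do not support taking this further. The 12% comes from one first-line monotherapy study and would be applied to both cohorts. No share of late onset is given. Related events of days 31 to 100, which are already meant to be summarised, would have to be removed. The number affected therefore remains unknown.

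No primary-endpoint figure or decision rule changes. The correction is worth making because it is cheap and decides whether the report can summarise late immune toxicity at all.

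**What to change.** 1. Correct SAP 4.3.1 and 4.4.8.1 so that they agree with Protocol 4.2.3 and with the SAP's own schedule: long-term follow-up also collects immune-mediated manifestations.
2. Record each positive follow-up answer with onset date, grade, attribution, and whether and when new anti-cancer therapy began. The existing immune-event eCRF page could serve.
3. Add one table of immune-mediated events by cohort and onset period (to day 30, days 31–100, after day 100 from the last dose), regardless of attribution, with events after new anti-cancer therapy shown separately.
4. Reconcile Protocol 8.3.1 and schedule footnote 4 with 8.2.5 on AESIs of days 31 to 100. The day-100 phone contact already offers the occasion to ask.

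Extending the collection of all SAEs to day 100 is optional. It would lengthen the 24-hour reporting duty and bring in events that follow next-line therapy.

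The cost of items 1 to 3 is wording, one table and limited extra data entry, with no new contact or procedure. If item 4 is settled in favour of recording every AESI to day 100, some additional expedited AESI reports follow.

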4.3.2 Missing or Partial Dates

All data will be listed and summarized as captured in the electronic Case Report Form (eCRF) or transferred from external sources (e.g., lab, ECG). It may be necessary to impute incomplete dates to correctly assign events to a period or to calculate durations.

For prior and concomitant medications, AEs, and cancer history dates the following rules will apply:

Missing	Rule for start date	Rule for end date	Flag for imputation
Day	First of month	Last of month*	D
Month [†]	1 January	31 December*	M
Year [†]	First Treatment Date	Date of Data Cutoff/Lock	Y

* Unless the imputed start date is before first visit date, in which case first visit date is used; or the imputed stop date is after last visit date in which case last visit date available is used.

† It is assumed that a missing Month implies a missing Day as well, and that a missing Year implies a missing Month and Day.

If the imputation of an AE start date leads to a date prior to the date of first vaccination, and it is possible that the AE start date can be on or after date of first vaccination based on partial date information (e.g., occurred on the same month), it will be set to the date of first vaccination to be conservative. In the event the imputation of an end date leads to a date after the death date of a subject, the death date will replace the imputed date.

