Before the Food and Drug Administration (FDA) approval of programmed death-1 (PD-1)/programmed death ligand-1 (PD-L1) inhibitory antibodies in 2016 and 2017, chemotherapy was the only treatment available for locally advanced or metastatic urothelial bladder cancer. The most efficacious chemotherapy regimens are those containing cisplatin, which represents a challenge for frail and unfit patients. Low performance status, advanced age, compromised renal function and comorbidities limit the capability of these patients to cope with intensive platinum-based regimens. A first step in selecting the proper treatment for UC patients is to identify to which category they belong, cisplatin eligible or ineligible. The category of cisplatin eligible patients is especially relevant for first-line treatment, since the administration of standard regimens such as DDMVAC [dose-dense methotrexate, vinblastine, doxorubicin and cisplatin] or cisplatin/gemcitabine is associated with a fraction of long-term survivors. However, the prognosis is dismal for patients with disease progression after first-line chemotherapy. The ORR was lower than 10% for all the single agents tested. No chemotherapy agent was ever approved by the FDA for second-line treatment and only vinflunine achieved the approval by the European Medicines Agency (EMA), based on a modest 2-month and non-statistically significant prolongation of OS in a randomized Phase 3 clinical trial (Balar et al., 2017a), (Bellmunt et al., 2009). A prognostic model was derived from the vinflunine pivotal trial database in which the most important prognostic factors were ECOG Performance status higher than 0, hemoglobin level less than 10 g/dL and liver metastasis (Bellmunt et al., 2010). Time from prior chemotherapy was later identified as an additional independent prognostic factor and accordingly it was recommended as a stratifying factor in randomized clinical trials (Sonpavde et al., 2013). In a poster communication to the (ASCO) Annual Meeting 2014 (Sonpavde, 2014), twelve Phase 2 clinical trials studying single agents or combinations included 711 patients and the global median OS was 6.8 months, 95% C.I. 6.2 to 7.3 months, with a range of 3.9 to 10.8 months. The median OS reported in the Phase 3 clinical trial that compared vinflunine versus investigator's chemotherapy choice were 6.9 and 4.6 months respectively (Balar et al., 2017a), (Bellmunt et al., 2009).

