4.4.7.5 Bladder Cancer History and Baseline Disease Characteristics

Variables

- Eastern Cooperative Oncology Group (ECOG) Performance Status (0, 1, ≥ 2)
- Time from Initial Diagnosis to First Treatment (years)
- Duration of Primary Curative Intervention (months)
- Disease Free Interval (months)
- Time from Recurrence after a Disease-Free Interval to First Treatment (years)
- Primary Tumor Site (Renal Pelvis, Ureter, Urethra, Urinary Bladder, Other)
- Stage at Diagnosis (I, II, III, IV)
- T Category (T_x, T₀, T_a, T_{is}, T₁, T_{2a}, T_{2b}, T_{3a}, T_{3b}, T_{4a}, T_{4b})
- N Category (N_x, N₀, N₁, N₂, N₃)
- M Category (M₀, M₁)
- PD-L1 tumor proportion score (TPS; < 1%, $\geq 1\% - 10\%$, $\geq 10\%$)
- Current Metastatic Disease Sites (Yes, No)
 - Sites of Current Metastatic Disease: Adrenals, Bone, Bone Marrow, Chest Wall, Central Nervous System/Brain, Fallopian Tubes, Kidney, Large Intestine, Liver, Lung, Lymph Nodes, Pancreas, Peritoneum, Pleura, Rectum, Small Intestine, Spleen, Stomach, Uterus, Other

Analyses

Missing dates for cancer history will be imputed per Section 4.3.2. Frequencies and percentage of subjects will be tabulated for categorical variables by cohort and overall. Percentages will be

based on the total number of subjects in the FAS within each cohort. The following formulas will be used to calculate the above time-specific variables:

Time from Initial Diagnosis to First Treatment = (Date of First Treatment – Date of Initial Diagnosis + 1)/365.25

The following will be included only in subject-level listings:

Duration of primary curative intervention in months = (End Date of Primary Curative Intervention – Start Date of Primary Curative Intervention + 1)/30.4375

Disease-free interval in months = (Date of Recurrence – End Date of Primary Curative Intervention + 1)/30.4375

Time from Recurrence after a Disease-Free Interval to First Treatment in months = (Date of First Treatment – Date of Recurrence + 1)/30.4375

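### SAP 4.3.2 moves partially dated pre-trial events up to the trial's start, so time from diagnosis and the cancer-history intervals can be false

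*SAP*

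**What the plan says.** SAP 4.3.2 states its scope in one sentence: "For prior and concomitant medications, AEs, and cancer history dates the following rules will apply". For a start date, a missing day becomes the first of the month, a missing month becomes 1 January, and a missing year becomes the first treatment date. The footnote sets a floor for start dates, "Unless the imputed start date is before first visit date, in which case first visit date is used", and a cap for end dates, "the imputed stop date is after last visit date in which case last visit date available is used". No floor is stated for end dates.

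SAP 4.4.7.5 links cancer history to this rule: "Missing dates for cancer history will be imputed per Section 4.3.2". The dates then feed four derived intervals:

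- for time since diagnosis, "Time from Initial Diagnosis to First Treatment = (Date of First Treatment – Date of Initial Diagnosis + 1)/365.25";
- the length of the curative intervention, counted in months from its own start and end dates;
- for the gap between that intervention and relapse, "Disease-free interval in months = (Date of Recurrence – End Date of Primary Curative Intervention + 1)/30.4375";
- the interval from recurrence to first treatment, built the same way in months.

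The last three are confined to subject-level listings. Time from initial diagnosis is not.

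**The concern.** A first-visit floor suits events that can only start once the subject is in the trial. A cancer diagnosis, a recurrence and the start of an earlier therapy normally precede screening. For those, the floor replaces a known month and year with a date known to be false.

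The SAP recognises the issue for adverse events. A further paragraph in 4.3.2 moves an AE start to first vaccination only if the partial information makes that date possible. Cancer history has no such check. SAP Section 1 says the plan will be followed completely, and the protocol's Missing Data text leaves imputation details to the SAP, so a programmer has no stated ground for departing from the rule.

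At stake is the accuracy of the baseline description. Readers of a single-arm trial use that description to judge who was enrolled.

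**Working it through.** The documents give no figure to reproduce, so the rule is applied to illustrative dates.

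**Assumed inputs (not from the documents).** First visit is 1 Mar 2019 and first treatment 29 Mar 2019, a 28-day gap. That is the longest screening window in the SAP General Definitions. Diagnosis is Jun 2016, curative intervention Jul to Oct 2016, and recurrence Feb 2018, all with the day missing. Diagnosis and recurrence are single dates. Treating them as start dates is an inference.

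**Rule as written.** Start date = later of (imputed date, first visit). End date = last day of the month, with no floor.

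| Interval (SAP 4.4.7.5 formula) | Without floor | With floor |
|---|---|---|
| Diagnosis to first treatment | 1032/365.25 = 2.83 y | 29/365.25 = 0.08 y |
| Duration of curative intervention | 123/30.4375 = 4.0 mo | -850/30.4375 = -27.9 mo |
| Disease-free interval | 459/30.4375 = 15.1 mo | 852/30.4375 = 28.0 mo |
| Recurrence to first treatment | 422/30.4375 = 13.9 mo | 29/30.4375 = 0.95 mo |

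The negative duration arises because the start moves to March 2019 while the end stays in October 2016.

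**Bound.** With a gap of g days between first visit and first dose, a floored diagnosis always gives (g + 1)/365.25 years, whatever the truth. This is 0.041 for g = 14 and 0.079 for g = 28. Protocol 4.2.1 allows up to two re-screenings, so g can exceed 28 if the first visit means the initial screening.

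**Missing year.** Diagnosis is set to first treatment, giving 1/365.25 = 0.003 years. If a diagnosis were handled as an end date instead, it would go to data cutoff, which is after treatment and equally wrong.

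**Ambiguities tested.**

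- *First visit.* SAP Table 1 numbers Screening as visit 1. The SAP definitions and schedule call first vaccination Visit 1. Under the second meaning the floored value is 0.003 years instead of 0.08.
- *Footnote marker.* The asterisk is printed only on the end-date cells, although the first clause concerns start dates. If it is confined to those cells, diagnosis and recurrence dates stay put but the end of curative intervention moves to 1 Mar 2019. The disease-free interval is then -392/30.4375 = -12.9 months and the duration 974/30.4375 = 32.0 months. The missing-year row carries no asterisk, so its problem remains.

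**Effect on a cohort summary.** One affected subject like the example lowers the cohort mean by (2.83 - 0.08)/33 = 0.083 years in Cohort 1, or 2.75/35 = 0.079 in Cohort 2. If the true mean were 2 years (assumption), each 10 percentage points of partial dates would remove 0.10 x (2 - 0.08) = 0.19 years. The reported mean would run from 2.0 with none partial to 0.7 x 2 + 0.3 x 0.08 = 1.42 with 30% partial.

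**The case against.** **The text is ambiguous.** The marker sits on end-date cells, the first visit is undefined, and diagnosis is not literally a start date. This stands as a limit on certainty about the floor. It does not rescue the rule: each reading of the marker and of the first visit gives a wrong result for some pre-trial date, and the missing-year result holds under all of them.

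**The reach is small.** This stands. Three of the four intervals appear only in listings. SAP 4.4.7.7 classifies prior medication by end date, so moving a start date does not change that class. SAP 4.3.2 also lists data as captured and flags imputed dates, so affected records can be found. The flag does not correct the summary table.

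**Stronger readings.** A reader might infer three things that the documents do not support:

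- *That every imputed pre-trial date moves to screening.* On the footnote's wording, only start dates have a floor.
- *That a known prognostic factor is corrupted.* Protocol 2.1 says "Time from prior chemotherapy was later identified as an additional independent prognostic factor", but no such variable is derived in the SAP, and its natural anchor would be an end date.
- *That the test against the 23% and 15% null rates is compromised.* That test uses response counts against fixed rates. Neither document plans a comparison of time from diagnosis with the historical patients.

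**Conclusion.** The rule is wrong as written for events that precede the trial. Through SAP 4.4.7.5, a partially dated diagnosis yields about 0.08 years or less unless re-screening puts the first visit more than 28 days before dosing. A diagnosis with missing year yields 1 day. In listings, the duration of curative intervention can turn negative and the disease-free interval can be distorted in either direction, depending on how the footnote is read.

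The effect is limited to the baseline summary of time from diagnosis and to the listing-only intervals. ORR, PFS and OS are not affected by this clause. The size in practice depends on how many dates are partial, which the documents do not say. The example dates, the 2-year mean and the 30% share are assumptions. The first-visit values (0.08 and the table above) rest on reading the footnote's first clause as a floor for start dates. The missing-year result does not. This should be corrected before programming, but it does not bear on the trial's conclusions.

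**What to change.** In SAP 4.3.2:

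1. Exempt cancer-history and prior-therapy dates from the first-visit floor. Keep the first of the month for a missing day and 1 January for a missing month, capped so that diagnosis, intervention, recurrence and first treatment stay in logical order.
2. Where the year is unknown for these dates, leave the date and any interval derived from it missing, and report the number missing.
3. Put the asterisk on the cells that the footnote governs, and define the first visit as either Screening or first vaccination.

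With item 1 the example returns 2.83 years, 4.0, 15.1 and 13.9 months. Mid-month or mid-year imputation would also be acceptable but is not needed.

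The cost is about two lines of SAP text, the footnote correction, and a matching change in the date-derivation program. No new data are needed.
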